In healthy, men and women aged 55 to 79 years, 6 weeks of supplementation with 1,000 mg/day of NR was well-tolerated and increased NAD+ levels in peripheral blood [10]. Importantly, NR supplementation produced trends towards reductions of SBP as well as arterial stiffness compared to placebo [10]. A post-hoc analysis of the same study sample showed trends towards larger reductions after NR supplementation in individuals with higher SBP (9 mmHg lower after NR compared to placebo among participants with 120–139 mmHg SBP) and arterial stiffness (41.5 centimeters per second (cm/s)) [10]. We believe that promising results from Martens et al., study and promising preclinical evidence from Das et al., that showed a combination of NAD+ replenishment and exercise was an optimal strategy to most effectively improve vascular function and reduce SBP in older mice, support our novel proposal that a combination of NR and aerobic exercise (NREx) will be more effective than either NR or exercise alone (exercise and placebo - PLEx) in hypertensive older adults. Thus, our central hypothesis is that the intervention of aerobic-exercise training combined with NR supplementation will reduce SBP in older adults who have high SBP more effectively than will exercise alone.

To test our central hypothesis, we will recruit 54 older adults ≥ 55 years old with high 24-hour average SBP and follow them for 6 weeks in a double-blind fashion. Participants will be randomly assigned to receive either (1) 1,000 mg/day of NR plus 3 days/week of supervised, center-based walking exercise, or (2) the same exercise program combined with placebo, or (3) 1,000 mg/day of NR alone. Inclusion of all treatment groups will be important for detecting the potential benefit of NREx. High SBP will be determined at screening as daytime average above or equal to 130 mmHg and below 160 mmHg, measured by the 24-hour BP device. All enrolled participants will undergo daytime continuous SBP measurements at baseline, 3 weeks, and 6 weeks, and arterial-stiffness measurements by pulse-wave velocity (PWV) at baseline and 6 weeks.

5. Specific Aims:

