Arterial Stiffness	Aortic pulse-wave velocity (PWV), commonly measured as carotid to femoral PWV (cfPWV), is considered to be the gold standard method of assessing arterial stiffness in humans. cfPWV will be measured using the SphygmoCor XCEL system (AtCor Medical, New South Wales, Australia). Briefly, cfPWV will be determined by recording pressure pulse waves at the carotid and femoral arteries using a high-fidelity micromanometer (Millar Instruments, Houston, TX) and calculating the distance between the recording sites divided by the time delay between the carotid and the femoral pulse waves [13].

6.10 Sample size justification. This pilot study will help generate precise estimates of effect variance in the population in which a subsequent larger-scale study will be conducted. Published recommendations for the design of pilot studies indicate that a sample of 18 participants per randomized arm is typically sufficient to estimate a parameter for a future trial [14-16]. The enrollment sample of 54 (n=18 x 3 arms) participants is intended to provide preliminary data necessary to indicate feasibility of a larger trial and to provide descriptive estimates of effects. Based on our experience from the past and current clinical trials conducted at our institute, we do not expect an attrition higher than 15%, therefore, we increased a group size to n=18, which will give us sufficient sample sizes for the pilot purposes after drop-out (n=15 x 3 groups). The data will also provide for nominal estimation (using a 95% CI) of mean changes in dependent variables within each arm. By assuming the mean decrease in SBP after a 6-week of intervention to be 20 mmHg, 10 mmHg and 15 mmHg in the three groups of NREx, PLEx and NR, respectively, and the standard deviation of the SBP decreases to be 10 [16], the sample size of 15 participants for each group can guarantee a power of 85% to detect the difference between the NREx and PLEx groups and a power of about 80% to detect the differences among the three groups. We expect that the differences of the arterial-stiffness measurements among the three groups are larger than those of SBP. Thus, the power numbers for that measure will be larger as well.

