10. Statistical Analysis Plan

The primary analysis will follow an “intent-to-treat” model. Because repeated measures are obtained on individual participants and they are potentially correlated, a mixed-effect linear regression model will be used. Differences in outcome measures at the 3-week follow-up (or 6-week close-out) from baseline for each individual participant will be used as responses, and two dummy variables representing the three treatment groups, age, and gender, and other baseline characteristics of participants will be used as covariates. A random-effect term will also be included in the model to accommodate within-subject data correlation. This analysis will be performed for each outcome variable. The relatively small sample size may imbalance pre-randomization covariates. Thus, caution will be taken in the interpretation of hypothesis testing results.

Literature cited

6. de Picciotto NE, Gano LB, Johnson LC, Martens CR, Sindler AL, Mills KF, et al. *Nicotinamide mononucleotide supplementation reverses vascular dysfunction and oxidative stress with aging in mice*. Aging Cell, 2016. **15**(3): p. 522-30.

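### The power of about 80% that 6.10 gives for the three groups does not follow from its inputs at 5%: an overall test has about 65%, and NREx versus NR has 26% to 38%

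*Combined protocol and SAP*

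**What the plan says.** Section 4 (Background) proposes that NREx "will be more effective than either NR or exercise alone (exercise and placebo - PLEx) in hypertensive older adults". The next sentence gives a narrower central hypothesis, that the combination lowers SBP more than exercise alone does. The opening summary states the same narrower hypothesis.

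Section 6.10 takes the mean decreases to be "20 mmHg, 10 mmHg and 15 mmHg in the three groups of NREx, PLEx and NR, respectively", with an SD of 10. It says that "the sample size of 15 participants for each group can guarantee a power of 85" per cent for NREx versus PLEx, and adds "a power of about 80% to detect the differences among the three groups". It gives no power for NREx versus NR, and no alpha or sidedness for either power figure.

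Section 10 fits a mixed model with "two dummy variables representing the three treatment groups", plus age, gender and other baseline covariates. It names no pairwise contrast and no overall test.

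**The concern.** The three-group statement can be read in two ways: as the power of one overall test, or as the power to separate the arms from each other, including NREx from NR. At 5% the first reading overstates the power, and the second overstates it by far more.

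The second reading matters because of the Background proposal. To be better than either component, NREx must beat the stronger one, and on the planning values that is NR (15 mmHg) rather than PLEx (10 mmHg). The limiting contrast is therefore 5 mmHg, half of the 10 mmHg behind the 85%. A significant overall test would not settle it, because that test can be significant through NREx versus PLEx alone. Section 10 does not say which contrast supports which statement, so nothing in the plan guards against that step.

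**Working it through.** **Inputs (all from 6.10).** Mean falls: NREx 20, NR 15, PLEx 10 mmHg. Common SD 10. Analysed n = 15 per arm, from 18 enrolled with up to 15% attrition (18 × 0.85 = 15.3). Alpha is not stated, so 5% is assumed, and pairwise tests are computed both one- and two-sided.

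**Step 1. Reproduce the 85% for NREx versus PLEx.** The standard error of a difference is 10 × √(2/15) = 3.65 mmHg. The noncentrality is 10 / 3.65 = 2.74 on 28 df.
- One-sided 5% (critical t 1.701): power 84.8%.
- Two-sided 5% (critical t 2.048): power 75.3%.

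At 15 per arm the stated 85% therefore corresponds to a one-sided 5% test. A two-sided test comes close only at the enrolled 18 per arm (83.0% by t, 85.1% by normal approximation).

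**Step 2. Overall three-group test.** The grand mean is 15, so the squared deviations sum to 25 + 0 + 25 = 50. The noncentrality is λ = n × 50 / SD² = 15 × 50 / 100 = 7.5, with F on 2 and 42 df (critical value 3.22). Power is 65.4%. With 18 per arm, λ = 9.0 and power is 74.4%.

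**Step 3. NREx versus NR.** The noncentrality is 5 / 3.65 = 1.37 on 28 df.

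| n per arm | two-sided 5% | one-sided 5% |
|---|---|---|
| 15 | 26.2% | 37.9% |
| 18 | 30.8% | 43.1% |

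**Step 4. NREx better than both comparators.** By simulation at 15 per arm (pooled SD, 42 df), both contrasts are significant in about 25% of trials two-sided and 37% one-sided. With a separate SD for each pair, the two-sided figure is about 24%.

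**Step 5. What a significant overall test says about NR.** Among simulated trials (15 per arm) with a significant F test at 5%, about 61% show no significant NREx advantage over NR at two-sided 5%, and 48% at one-sided 5%.

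**Step 6. Precision.** The expected 95% CI half-width for a pairwise difference is 2.048 × 3.65 = 7.5 mmHg, wider than the planned 5 mmHg.

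**The case against.** The strongest reply is that the plan never promises a powered NREx versus NR test. The wording about either component is a Background proposal, and the central hypothesis that follows it names exercise alone. Section 8 mentions superiority to both only as something that may happen. Section 5 sets the aims as obtaining data to size a full trial, 6.10 says the sample is for feasibility and descriptive estimates, and Section 10 asks for caution in interpreting tests. All of this stands. A reader might infer that the trial fails to deliver something it committed to, but the documents do not support that.

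Second, 26% alone would be unfair. Alpha and sidedness are not given, and the convention that reproduces the plan's 85% gives 38%. This also stands, so the range is reported.

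Third, the three-group figure may rest on another convention. An overall F test at 10% with 15 per arm gives 76.8%. A two-sided 5% normal-approximation test of a linear trend across 10, 15 and 20 gives 78.2%, but that is the NREx versus PLEx contrast over again. Either could loosely be called about 80%. Neither test is specified, and neither supports a statement about NREx versus NR. Repeated measures and covariates in the Section 10 model might add power, but 6.10 makes no allowance for them and gives no correlation from which to calculate it.

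Fourth, a reader might infer that results will be misreported as superiority to both components, or that Aim 1 will size the full trial on the easier contrast. The documents say neither, and Aim 1 names no contrast. The choice still matters: at 80% power and two-sided 5%, 10 mmHg needs 17 per arm and 5 mmHg needs 64.

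**Conclusion.** The point holds as a correction to a stated figure and a limit on the conclusion. At 5%, with SD 10 and 15 per arm, the power in 6.10 for the three groups is about 65% as an overall test. For NREx versus NR it is 26% (two-sided) to 38% (one-sided), and for NREx beating both comparators about 25% to 37%. Even with all 18 per arm analysed, the overall test reaches 74% and NREx versus NR reaches 31% to 43%, so no 5% convention tried brings either to 80%. These results rest on the plan's own means and SD, a common SD across arms, and an assumed 5% level.

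It does not follow that the design is unfit. NREx versus PLEx is the central hypothesis and the one pairwise contrast that 6.10 powers, and a pilot need not power the other two.

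**What to change.** **Section 6.10.** State alpha and sidedness. Replace the figure of about 80% with the recomputed three-group power (about 65% for an overall F test at 5%, 15 per arm), or name the test and level that produced it. Add the NREx versus NR power: 26% two-sided, 38% one-sided.

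**Section 10.** Name NREx minus PLEx as the contrast for the central hypothesis. This is mainly clarification, since Section 4 already implies it. Report NREx minus NR and NR minus PLEx as estimates with 95% CIs, noting the expected half-width of about 7.5 mmHg.

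**Conclusion.** State in Section 10 that superiority to both components will not be concluded from an overall test, from NREx minus PLEx alone, or from point estimates that merely favour NREx. The last exclusion is needed because, in simulation at 15 per arm, NREx has the largest fall in 33% of trials when all three arms are equal, and in about 50% when NREx equals NR and PLEx is 10 mmHg worse.

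**Cost.** Wording changes and a less favourable stated power. No added participants, visits or procedures.

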More than 80% of older adults have hypertension, with higher prevalence of high systolic blood pressure (SBP) putting them at high risk for cardiovascular (CV) disease and death. Because drug therapy that lowers SBP is associated with side effects such as hypotension, syncope, and kidney dysfunction, there is a great need for effective lifestyle SBP-lowering interventions for the older population that can replace drug therapy. While aerobic exercise is a recommended lifestyle intervention for controlling SBP and preventing CV disease naturally, in older adults it has been shown to be less effective in vascular-tissue remodeling because of arterial stiffness, resulting in less efficient SBP control. Reduced bioavailability of nicotinamide adenine dinucleotide (NAD+), a cofactor for the deacetylase sirtuin1 (SIRT1), may contribute to age-related vascular dysfunction via oxidative stress and reduced nitric oxide (NO). Exercise-induced overexpression of NAD+-dependent SIRT1 improves the bioavailability of NO. Preclinical evidence suggests that poor vascular-function improvement in response to exercise in older mice is caused by insufficient NAD+ levels to stimulate SIRT1 activity. Importantly, replenishment of NAD+ levels induced vascular remodeling, improved vascular function, and reduced SBP in mice. An objective of this study, therefore, is to test a combination of aerobic exercise and nicotinamide riboside, a compound that replenishes NAD+ levels, to optimize exercise's SBP-lowering effect in hypertensive older adults. Initial human clinical trials demonstrated that nicotinamide riboside supplementation (1,000 mg/day) was safe and showed a higher potential to reduce SBP and arterial stiffness in participants with elevated SBP. As we have preclinical evidence that combining NAD+ replenishment with exercise is an ideal strategy for improving vascular function, our central hypothesis is that the intervention of aerobic-exercise training combined with nicotinamide riboside supplementation will reduce SBP in hypertensive older adults more effectively than will exercise alone. We will enroll 54 participants \geq 55 years and older into either: (1) 1,000 mg/day of nicotinamide riboside plus 3 days/week of supervised, center-based walking exercise (n=18), or (2) the same exercise program combined with placebo (n=18), or (3) 1,000 mg/day of nicotinamide riboside alone (n=18). All participants will undergo daytime continuous SBP at baseline, 3 weeks, and 6 weeks, and arterial-stiffness measurements by pulse-wave velocity at baseline and at 6 weeks. Elevated SBP will be determined as daytime average equal to or above 130 mmHg, measured by the 24-hour blood-pressure device. To our knowledge, this study will be the first attempt to enhance exercise therapy with nicotinamide riboside in hypertensive older adults. We believe that nicotinamide riboside is "the missing piece of the puzzle" in improving vascular remodeling and SBP management in older adults. Preliminary evidence from this pilot study may support a full-scale Phase III clinical trial in hypertensive older adults. The ultimate goal of this line of research is to find adjuvant strategies to improve the exercise's SBP-lowering effects in older adults.

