The objective of this study is to conduct a pilot study to refine and finalize elements critical to conducting a future, definitive randomized, controlled trial (RCT). We propose to recruit 54 persons aged ≥ 55 years with SBP ≥ 130 mmHg and < 160 mmHg for 6 weeks. Participants will be randomly assigned to receive either (1) 1,000 mg/day of NR plus 3 days/week of supervised, center-based walking exercise, or (2) the same exercise program combined with placebo, or (3) 1,000 mg/day of NR alone. Inclusion of all treatment groups will be important for detecting the potential benefit of NREx. High SBP will be determined at screening as daytime average above or equal 130 mmHg and below 160 mmHg, measured by the 24-hour BP device. All enrolled participants will undergo daytime continuous SBP measurements at baseline, 3 weeks, and 6 weeks, and arterial-stiffness measurements by pulse-wave velocity (PWV) at baseline and 6 weeks. This study will enable us to address the following aims, all of which are of critical importance for designing a full-scale trial.

Aim 1. To obtain critical data necessary to project the sample size needed for a full-scale trial using the change in SBP, as the primary outcome and;

Aim 2. Using the change in arterial stiffness, as the secondary outcome.

6. Research Plan:

We propose to conduct a randomized, controlled pilot trial to test if nicotinamide riboside improves an effect of aerobic exercise training on cardiovascular function among hypertensive older adults. Following study entry, participants (N = 54) will be randomly assigned to either NREx, NR or PLEx groups for 6 weeks. Exercise groups will be involved in three center-based walking training sessions per week. We anticipate that up to an additional 20 individuals enrolled may discontinue participation in the project prior to completion, and that we may have to screen up to 250 additional individuals to reach our recruitment goal of 54 subjects.

6.1 Participants: Eligible participants will be males or females ≥ 55 years of age with daytime average SBP ≥ 130 mmHg and < 160 mmHg.

Table 3.1.1. Inclusion and exclusion criteria.

Inclusion Criteria

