
• Age 55 years and older• Daytime average of systolic blood pressure of ≥ 130 mmHg and < 160 mmHg.• Sedentary lifestyle, defined as < 150 min/wk of moderate physical activity as assessed by the CHAMPS questionnaire.• Willingness to be randomized to either treatment group• Willingness to participate in all study procedures
Exclusion criteria

• Failure to provide informed consent.• Pregnant• Change in blood pressure therapy (type or dose) within the last 3 months- Temporary Exclusion• Daytime average of systolic blood pressure ≥ 160 mmHg.• Regular consumption of nicotinamide riboside supplement• Current involvement in supervised rehabilitation program

- Absolute contraindication(s) to exercise training according to American College of Sports Medicine guidelines [11]
- Daytime average of systolic blood pressure below 130mm Hg or Diastolic BP \geq 100mm Hg.
- Peripheral vascular disease; peripheral neuropathy; retinopathy
- Severe cardiac disease, including NYHA Class III or IV congestive heart failure, clinically significant aortic stenosis, history of cardiac arrest, use of a cardiac defibrillator, or uncontrolled angina;
- Myocardial infarction or stroke within past year
- Significant cognitive impairment, including known dementia diagnosis or a Mini-Mental State Examination exam score < 24
- Progressive, degenerative neurologic disease, e.g., Parkinson's Disease, multiple sclerosis;
- Severe rheumatologic or orthopedic diseases, e.g., awaiting joint replacement, active inflammatory disease;
- Severe pulmonary disease, requiring steroid therapy or the use of supplemental oxygen;
- Hip fracture, hip or knee replacement, or spinal surgery within past 4 months;
- Other significant co-morbid conditions that would impair ability to participate in the exercise-based intervention
- Simultaneous participation in another intervention trial

6.2 Recruitment: Participant recruitment will be coordinated in conjunction with the *OA/C Clinical Research Core*, led by co-investigator [name]. We will develop a targeted recruitment approach based on previous experiences utilizing methods of recruitment that include direct mailings, newspaper classified and print ads, community luncheons and health fairs, as well as clinic referrals. We have been extremely successful in implementing this approach in past studies

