will be measured, as well as exercise capacity with the 6-Minute Walk Test and self-assessed functionality with the Late Life Function and Disability Instrument (LLFDI). Participants will also be given the 24-h BP device to complete the 24-hour ambulatory recording and will have their arterial stiffness assessed. We will also collect adverse events and update medication changes. Finally, the study coordinator will provide participants with a supplement intake form to take home to record when the supplement is taken. Staff members will then discuss randomization procedures with participants. The participants will receive a return envelope/box to return the ambulatory BP device after the 24-hour recording.

6.5 Exercise Intervention: After random assignment to either the NREx or the PLEx groups, participants will engage in a three-days a week, center-based walking exercise intervention for 6 weeks. Following a brief warm-up, participants will be instructed to walk for 30 minutes at a 5-6 on the CR10 scale with encouragement for 10 minutes to be vigorous (7-8 on CR10 scale). Sessions will also include balance training to promote cool-down. Participants will be introduced to exercises in such a way that they begin with lighter intensity and gradually increase. The progressive nature of the intervention is designed to minimize discomfort and prevent injury. Blood pressure will be measured prior to each exercise session; the participant will not complete the session that day if he or she has an in-person SBP >200 mmHg or DBP >110 mmHg (AHA guidelines for exercise contraindication) measured at the exercise center.

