6.6. Supplementation: Participants will be randomly assigned to receive, in a double-blind fashion, either 1,000 mg/day of encapsulated NR (Niagen®) or placebo. The company ChromaDex (Irvine, CA) will provide both the NR and placebo capsules for the proposed study. Placebo capsules will be identical to those including NR. As noted above, a 6-week NR study of Martens et al. demonstrated that NR supplementation at a dose of 1,000 mg/day was safe in rather healthy middle-aged and older adults. Subjects will ingest NR (NIAGEN®; 500 mg, twice per day; ChromaDex, Inc.) or alike looking placebo capsules [10]. The participants will be provided with capsules sufficient for at least 3 weeks. The second 3-week portion of the capsules will be dispensed at 3-week follow-up visits by a study coordinator. A study coordinator will be given a jar with the study product by an unblinded staff person not-involved in this study. The not-involved staff member will be in possession of the identified randomization list and will provide this list after completing the enrollment and outcome measure analyses. The participants will receive a supplement intake diary to note the taken pills and a study coordinator will count the remaining pills at 3 and 6-week visits.

Data from the exercise interventions will be collected and stored in the study database. Following each session, participants will be asked to provide a rating of perceived exertion (RPE) for the session according to the Borg CR10 scale.

Table 1. Data collection summary by study visit.

Study phase	Pre-randomization		Randomization	
Visit description (FU=follow-up, CO=close-out)	Screen	Baseline	FU	CO
Visit number	1	2	3	4
Week number	-2	0	3 (+ or - 7 days)	6 (+ or - 7 days)
Informed consent, review of inclusion/exclusion criteria	X			
Medical history and medications, MSSE	X			
Height	X			
Weight	X	X	X	X
BMI (calculated in database only)	X			
Demographics information	X			
Physical Exam/nursing assessment	X*	X*		
Monitor vital signs	X	X	X	X
Ambulatory BP recording	X	X	X	X

CHAMPS Questionnaire	X			
Pregnancy test	X			
6 minute walk test		X		X
Late Life Function & Disability Instrument		X		X
Randomization		X		
Blood collection		X	X	X
Urine collection		X	X	X
Arterial stiffness		X		X
Dispense Supplement Intake Diary		X	X	
Dispense Study Supplement (NR or Placebo)		X	X	
Pill counts, collect diaries, assessment of adverse experiences			X	X
Collection of AEs and update medication changes		X	X	X

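### Double-blind is claimed for all 54 participants, but placebo is given only with exercise, so the supplement is not masked in the NR-alone arm (18 of 54)

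*Combined protocol and SAP*

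**What the plan says.** Section 4 (Background) applies the blinding claim to the whole cohort: 54 people will be recruited, and the plan is to "follow them for 6 weeks in a double-blind fashion". Section 6.6 (Supplementation) repeats it for the capsules: "Participants will be randomly assigned to receive, in a double-blind fashion, either 1,000 mg/day of encapsulated NR" or placebo. Neither place excepts an arm. Section 6.6 adds two safeguards: the placebo capsules look the same as the NR capsules, and the randomization list stays with a staff member outside the study, who "will provide this list after completing the enrollment and outcome measure analyses".

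The abstract and sections 4 and 5 list the arms. After NR plus exercise come "2) the same exercise program combined with placebo, or (3) 1,000 mg/day of NR alone". The abstract gives 18 participants to each. Section 6.5 confirms that only two arms exercise: "After random assignment to either the NREx or the PLEx groups, participants will engage in a three-days a week, center-based walking exercise intervention". No arm receives placebo without exercise.

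The central hypothesis (abstract and section 4) compares NREx with exercise alone. Section 4 also expects the combination to do better than NR alone. The SAP (section 10) enters the three groups as two dummy variables and names no primary contrast.

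**The concern.** Identical capsules and a sealed list mask the supplement only if something else about a participant does not give it away. Here exercise status does. Supervised sessions at a center three times a week cannot be hidden, and not having them goes with only one supplement.

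The plan therefore claims a property that one of its three arms does not have. A reader of the results would take every between-arm comparison as double-blind, including those with NR alone. The pilot is meant to inform a definitive trial, so an inaccurate description of the masking could be carried into that design. The SAP does not separate the one supplement-masked comparison from the other two.

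**Working it through.** **1. Arm counts.** Section 6.10 wants 15 completers per arm and allows 15% attrition: 15 / (1 − 0.15) = 17.6, rounded up to 18 per arm, and 18 × 3 = 54. The plan's enrolment figure reproduces.

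**2. What exercise status reveals about the capsule.** The inputs are the three arms and their sizes (abstract; sections 4, 5 and 6.5).

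- Among those who exercise (NREx 18, PLEx 18), the share on NR is 18 / 36 = 50%. Exercise status says nothing about the capsule.
- Among those who do not exercise (NR alone 18), the share on NR is 18 / 18 = 100%. The capsule is known.

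The supplement can therefore be deduced for 18 / 54 = 33% of participants, who are 18 / 36 = 50% of all NR recipients.

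**3. Who can make the deduction.** It requires knowing the three-arm layout and whether the person exercises.

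- *Staff.* They work from this protocol, which sets out the layout. No section says that coordinators or assessors are kept unaware of exercise assignment. Withholding the list does not help, because the list is not needed.
- *Participants.* They know whether they exercise. Whether they know the layout is an inference. An inclusion criterion in section 6.1 is "Willingness to be randomized to either treatment group", section 6.4 has staff discuss randomization procedures with them, and the paragraph on adherence says they are informed of what the study requires before randomization. None of this says outright that all three arms are described, and the consent pages are not in the reviewed text.

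**4. Each contrast in turn.**

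| Contrast | Exercise | Supplement |
|---|---|---|
| NREx vs PLEx | same in both arms | masked in both arms |
| NR vs PLEx | differs, visible | deducible on the NR side |
| NREx vs NR | differs, visible | NR in both arms |

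One contrast of three is masked for the factor that distinguishes its arms. NR vs PLEx is open for exercise and also, on the NR side, for the capsule. NREx vs NR is open because exercise is visible. That is inherent to an exercise trial and would remain true if a placebo arm without exercise were added.

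**5. Bias.** The documents give neither its size nor its sign, so no figure is computed. No sample-size or power figure changes because of this point.

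**The case against.** The strongest reply is that the claim is loosely worded but aimed at the right comparison. The sentence in section 4 opens by referring to the central hypothesis, which is NREx vs exercise alone, and that contrast is masked for supplement. Section 6.6 describes assignment to NR or placebo, with matched capsules and an independently held list. The documents also single out NREx vs PLEx elsewhere: it is the central hypothesis and the only pair with its own power figure (85%, section 6.10). The primary outcome is recorded by a device, the study is a pilot, and the SAP already urges caution with hypothesis tests.

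Most of this stands, and it limits the weight of the point. It does not remove it. The people to be followed double-blind are all 54, and neither the opening words nor the matched capsules exclude the NR-alone arm. Device recording limits the scope for assessor influence on blood pressure, but it does not make the design statement true.

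A reader might infer more, and the documents do not support it:

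- *That participants in the NR-alone arm certainly know their capsule.* This is likely, but the available text does not say they are told the layout.
- *That capsule knowledge makes NREx vs NR open.* Both arms take NR, and the openness comes from exercise.
- *That the study database reveals the arm, because "Data from the exercise interventions will be collected and stored in the study database".* The documents do not say how the database is organised or who sees it. Someone in an exercise arm who left before the first session would also have no session record.
- *That the main comparison is compromised.* It is not.

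**Conclusion.** The point holds as an inaccurate design statement affecting one arm. The supplement is not masked for 18 of 54 participants, although sections 4 and 6.6 say that it is. For staff this follows directly from the arm list, given that they know who exercises. For participants it rests on the assumption that they know the three-arm layout.

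The consequence is confined to how contrasts with NR alone may be described. Capsule knowledge adds to the visible exercise difference only in NR vs PLEx, which is not one of the hypotheses stated in the abstract or section 4. NREx vs NR, which section 4 does expect to favor the combination, cannot be called double-blind either, but only because exercise cannot be hidden. NREx vs PLEx, which carries the central hypothesis, is unaffected. Any bias is of unknown size and direction. The text should be corrected, but nothing here calls for a change to the arms or the sample size.

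**What to change.** 1. In sections 4 and 6.6, limit the claim to wording such as: *double-blind with respect to supplement for NREx vs PLEx; supplement is not masked in the NR-alone arm*.
2. In the SAP (section 10), name NREx minus PLEx as the primary contrast. This matches the central hypothesis and the pair for which section 6.10 states 85% power. That figure is cited here only to show which contrast the plan singles out; it is not checked here.
3. In the SAP, state that contrasts with NR alone will be reported as not blinded, for participants or staff, and as estimates with 95% confidence intervals.

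The cost is a few sentences in the protocol and SAP, with no new arm, procedure or participants. The one downside is that conclusions about NR alone, including the expectation in section 4 that NREx will do better, would be stated more weakly.
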